In most settings, laboratory diagnosis of infection has been based on real-time reverse transcriptase polymerase chain reaction (RT-PCR). Diagnostic RT-PCR typically targets the viral ribonucleic acid (RNA)-dependent RNA polymerase (RdRp) or nucleocapsid (N) genes using swabs collected from the upper respiratory tract (nose and throat).^{6,7} However, the requirement for specialist equipment, skilled laboratory staff, and PCR reagents has created bottlenecks. Clinical care and public health containment efforts are thus impeded by diagnostic delays even for clinically unwell patients, and further limited by a lack of wider testing including both mass screening, and specific high-risk groups (contacts of confirmed cases, and healthcare workers and their families). Further the numbers who are asymptomatically infected are currently completely unknown. Poor population-level data adds uncertainty to dynamic models that inform planning of lockdown restrictions (as exemplified by experiences in other countries⁸). Furthermore, even when available, RT-PCR from upper respiratory tract swabs may be falsely negative, due to quality or timing of collection; viral titres in upper respiratory tract secretions peak in the first week of symptoms,⁹ but may have declined below the limit of detection in patients who present with symptoms beyond this time frame.¹⁰ In individuals who have been infected and recovered, RT-PCR provides no information about prior exposure or immunity.

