These cross-sectional surveys will be repeated over time, recruiting new households each week, following standard sampling methods (for example as employed in the Labour Force Survey) to ensure that the study represents the UK population and can estimate reliably prevalence over time of symptomatic and asymptomatic infection and immunity (as assessed by various antibody profiles) (Figure 1). In each cross-sectional survey, up to protocol v15.0 study participants who provide additional optional consent/assent will undergo repeated serial sampling at 1, 2, 3 and 4 weeks (approximately 1 month) after their enrolment visit (week 0) to assess incidence of new infection, viral clearance and changes over time in immunity. If further additional consent is given, this will then be further repeated at month 2 and every month thereafter from their first study visit to assess these outcomes over the longer term. Up to protocol v15.0, the choice of participating once at enrolment, weekly for the first month, or weekly for the first month and then monthly will be made at the enrolment visit; participants will not be offered the option to extend if they initially choose weekly visits for one month only. Over 95% of participants offered these options through to protocol v15.0 chose to have repeated monthly visits over the longer term, and a number of those who initially chose 1 or 5 visits requested to then extend their participation (which was not possible under the approved protocol). Therefore from protocol v16.0, we will ask everyone joining the study to have study assessments every week for the first month and then every month until the study ends. Participants are free to withdraw at any time.

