- Email if participant would like to receive communication about the study (eg assessment window notifications) or test results (results will be returned by the study identified by month and year of birth only (not person-identifiable), or vouchers for participation directly by this route, and also to receive updates on results and news about the study (see Section 16.8). Participants may opt out of emails with updates on results from and news about the study, but may not opt out (unsubscribe) from emails about the study procedures or test results, or any communication about the study that has been approved by the Research Ethics Committee.

The following questions will be asked at each assessment (including the enrolment home visit up to protocol v15.0 and the first time the questionnaire is completed online or by telephone for new participants from protocol v16.0), with only changes (where relevant) being elicited at any follow-up assessments:

- Is the participant currently symptomatic or self-isolating? If self-isolating is this because of symptoms in self or others in the household
- Do they have any of the following symptoms today (yes/no for each of fever (including high temperature), muscle ache (myalgia), fatigue, sore throat, cough, shortness of breath (dyspnea), chest pain, headache, nausea/vomiting, abdominal pain, diarrhoea, loss of taste, loss of smell,

Clinical Research Protocol Template version 15.0

© Copyright: The University of Oxford and Oxford University Hospitals NHS Foundation Trust 2019 Page 56 of 113 trouble sleeping, loss of appetite/eating less than usual, runny nose/sneezing, noisy breathing (wheezing), chest pain, palpitations, vertigo/dizziness, memory loss/confusion, difficulty concentrating, worry/anxiety, low mood/not enjoying anything, other symptoms) or since the last visit, or otherwise consider that they currently have COVID-19

- Have they recently been in contact with someone that they definitely know (based on a positive test) or suspect (no positive test) was infected with COVID-19 at the time of contact? Yes/No for each type of contact and for each
 - If yes, date of last contact
 - o If yes, was this someone in their own household or someone outside their household
- Occupation (available from ONS or NISRA for the adult targeted in the original letter where identified from previous surveys, but not for the rest of the household or those identified through address lists)

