- Working status (employed, not working, retired, student etc) and work location (at home, outside of home etc), including number of days per week usually spent working outside the home or at school/nursery, and mode of transport to get to work/school/nursery
- Healthcare and social care contacts including currently working in health/social care in roles which primarily directly interact with patients/residents/clients or not, recently visited hospital or residential/nursing care home
- Contacts with other individuals inside the household (eg social distancing within the household) and outside the household, including through work, school/nursery, shopping, exercise etc including duration and number of individuals, how easy they find it to maintain social distancing and use of face coverings or masks
- Do they have long-term health problems, and do these limit their activities?
- Current smoking status
- Have they recently travelled abroad? If yes, to which countries?
- Have they received or been offered a vaccine against COVID-19? If yes, type, number of doses, dates.
- Have they received a vaccine against influenza? If yes, date.
- Do they think/know they have been infected by COVID-19? Yes/No
 - If yes, date first symptoms and what symptoms (yes/no for each of fever (including high temperature), muscle ache (myalgia), fatigue, sore throat, cough, shortness of breath (dyspnea), chest pain, headache, nausea/vomiting, abdominal pain, diarrhoea, loss of taste, loss of smell, trouble sleeping, loss of appetite/eating less than usual, runny nose/sneezing, noisy breathing (wheezing), chest pain, palpitations, vertigo/dizziness, memory loss/confusion, difficulty concentrating, worry/anxiety, low mood/not enjoying anything, other symptoms)
 - \circ If yes, did they contact the NHS about this (suspected) COVID-19 infection? Yes/No
 - If yes, were they tested? Yes/No
 - If tested, were they positive/negative/test failed/results not yet received?
 - If yes, were they hospitalised Yes/No?
 - If yes, do they think that they are suffering from "long COVID" and with what symptoms?
 How is this limiting their activities?

Household postcode (required at the level of outward portion and first number of the inward portion for geospatial analyses) will be available from the original ONS or NISRA survey or the address list from which the household was sampled. However, full address will also be confirmed against the household

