In addition, the proportion of individuals with symptomatic and asymptomatic infection (based on PCR of nose and throat swabs) based on the latest result in the last two weeks will be summarised approximately every calendar week from the start of the study, overall and by geographical region. Proportions will be calculated incorporating sampling weights for the original ONS and NISRA surveys, this survey and for non-response to this survey, with 95% confidence intervals estimated using the Korn-Grauberd method which allows for the low anticipated positivity rates. We will use Bayesian methods in sensitivity analyses assessing the impact of plausible ranges of test sensitivity and specificity on results, incorporating both the assay performance and the fact that participants are self-swabbing. Associations between various predictors and ever testing positive for infection vs never testing positive will be estimated using unweighted proportions and Fisher's exact tests with multivariable logistic regression models to adjust for confounding. Factors considered will include sex, ethnicity, age at last birthday (as both categorical and continuous variables) and other responses to the short questionnaire. These factors will also be considered in multi-level regression models, similar to the main model over continuous time described above.

Similar spatiotemporal MRP methods will be used to estimate proportions over time with immunity defined based on the optical density readings from the ELISA assay for IgG antibodies versus the threshold defined in comparison with pre-pandemic plasma. We will also estimate the proportions with previous infection (as defined by antibodies) but no previous symptoms.

Random effects linear regression models will also be generated for the absolute optical density readings (potentially log-transformed depending on the distribution) in relation to time since onset of first symptoms, with those not reporting symptoms treated as an additional category (random effect per household – may be omitted depending on model fit). Additional factors considered in these models will include age, sex and ethnicity.

Incidence will be calculated indirectly by deconvoluting the Bayesian dynamic multi-level regression model estimate of swab positivity and an estimate of duration of PCR positivity based on those testing positive in the study. More details are provided on

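### Symptoms before enrolment are asked only of people who think or know they had COVID-19, so the antibody-based symptom-free share is biased upward for infections that predate enrolment

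*Protocol*

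**What the plan says.** Protocol Section 11.2, after describing the model for antibody positivity over time, adds: "We will also estimate the proportions with previous infection (as defined by antibodies) but no previous symptoms". It does not say which questionnaire items define the absence of symptoms, and it does not limit the estimate to infections acquired during the study. The same section then models antibody optical density against time from first symptoms, with participants who report no symptoms kept as a category of their own.

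Section 9.6.1 contains two separate sets of symptom questions. Both fall under one introduction: "The following questions will be asked at each assessment (including the enrolment home visit up to protocol v15.0".

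- Asked of everyone: "Do they have any of the following symptoms today", followed by a long symptom list and the extension "or since the last visit, or otherwise consider that they currently have COVID-19".
- Asked behind a filter: "Do they think/know they have been infected by COVID-19? Yes/No", and only then "If yes, date first symptoms and what symptoms".

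On repeated contact, Section 7 reports: "Over 95% of participants offered these options through to protocol v15.0 chose to have repeated monthly visits over the longer term". Section 11.1 states that there is no formal statistical analysis plan. Section 11.2 refers to a methods page on the ONS website, which is not available for this review.

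**The concern.** The filter question measures what the participant believes or has been told about infection. The estimate in Section 11.2 claims something different, namely that symptoms were absent. Take someone who had a fever or cough before joining, put it down to another cause or could not be tested, and is antibody-positive at the first blood draw. That person answers No to the filter, is not asked for a symptom history, and enters the estimate as previously infected without symptoms. The error runs in one direction, upward.

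The problem is sharpest for early infections. Section 5 describes testing at that time as "further limited by a lack of wider testing including both mass screening, and specific high-risk groups", so people infected then had little basis for a Yes. The same section describes the number of asymptomatic infections as unknown, so a figure published under this label would be read as filling that gap. The optical-density model is exposed to the same misclassification if its time origin is the date of first symptoms collected behind the filter.

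**Working it through.** The plan states no figure for this estimate, so there is none to reproduce. The check has two parts.

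**1. Which question covers which period**

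| Period of the symptoms | Question in Section 9.6.1 | Who is asked |
|---|---|---|
| Day of any assessment | Symptom list, today | Everyone |
| Between two assessments | Same list, since the last visit | Everyone with an earlier visit |
| Before enrolment | Date and list of first symptoms | Only those answering Yes to think/know |

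Only the third row depends on belief. However Section 11.2 is read, no symptom source for the period before enrolment is free of it. For the period after enrolment there is one.

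**2. Size under stated assumptions**

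Notation:
- *a* = true symptom-free share among antibody-defined past infections
- *f* = share of symptomatic infections that predate enrolment
- *u* = share of those never recognised as COVID-19

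The documents give none of the three, so all are assumptions. Unrecognised symptomatic infections before enrolment are added to the truly symptom-free ones:

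recorded share = *a* + (1 − *a*) × *f* × *u*

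With *a* = 0.30:

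| *f* | *u* = 0.20 | *u* = 0.40 |
|---|---|---|
| 1 | 0.30 + 0.70 × 1 × 0.20 = 44% | 0.30 + 0.70 × 1 × 0.40 = 58% |
| 0.25 | 0.30 + 0.70 × 0.25 × 0.20 = 33.5% | 0.30 + 0.70 × 0.25 × 0.40 = 37% |
| 0 | 30% | 30% |

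The excess is 14 to 28 points when every symptomatic infection predates enrolment, 3.5 to 7 points when a quarter do, and nil when none do. A Yes given at a later assessment lowers *u*, and the excess falls in proportion.

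**The case against.** The strongest reply is that the questionnaire is better than the filter alone suggests. Everyone is asked about symptoms at every assessment, and Section 7 reports that over 95% chose repeated monthly visits, so symptoms during follow-up are recorded whatever the participant believes. This stands. A reader might infer that symptoms in general are asked only of people who believe they were infected; Section 9.6.1 does not support that.

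Second, the filter says think or know, is repeated at follow-up, and swab and anti-spike results are returned to participants (Section 9.9.2). A No at enrolment can become a Yes, and the symptom history is then asked. This also stands, but only in part. It relies on recall, tells a vaccinated participant little because anti-spike antibodies are then expected, and is closed to single-visit participants. It also makes the classification depend on what the participant has been told.

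Third, Section 11.2 does not say that it uses the filtered item. True, but this does not rescue infections before enrolment, since no other item covers them.

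Fourth, this is one subsidiary serological output. A reader might infer that the primary objective on symptomatic and asymptomatic infection is compromised. It is not: that objective rests on swabs (Section 6), and symptoms at and between visits are asked of everyone.

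Finally, a reader might take the bias to be 10 to 35 percentage points. That range comes from true shares of 30-50% with 20-50% unrecognised (0.50 + 0.50 × 0.20 = 60%, and 0.30 + 0.70 × 0.50 = 65%). It also requires every infection to predate enrolment and no answer to be revised later. It is an extreme case and does not describe the planned estimate.

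**Conclusion.** The point holds for antibody-positive participants whose infection predates enrolment. For them the planned symptom-free share counts unrecognised symptomatic infections as symptom-free and is biased upward. The category of participants not reporting symptoms in the optical-density model shares the error if it uses the filtered date of first symptoms. Infections acquired during follow-up are unaffected.

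The direction follows from the questionnaire; the size does not. The tabulated figures rest on an assumed true share of 30% and 20-40% unrecognised, and on how much of the antibody-positive group was infected before enrolment. Because Section 11.1 says there is no formal analysis plan, the definition belongs in Section 11.2. This is an inexpensive correction to a secondary estimate whose label claims more than the instrument can measure.

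**What to change.** Split the estimate in Section 11.2.

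- **Antibody conversion between consecutive study bloods, not explained by vaccination.** Define the absence of symptoms from the items asked of everyone (today and since the last visit). State which COVID-related symptoms count. The full list includes poor sleep, anxiety and low mood, and counting any of these over a month would push the share downward.
- **Already antibody-positive from infection at first blood draw.** Report as no recognised symptoms, or infection not recognised by the participant, and do not call it asymptomatic. Use the same label in the optical-density model.

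First-positive study swabs should not be merged into this estimate, because it is defined by antibodies; if reported, they belong in a separate line.

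The cost is text and a changed analysis set, with no new data. The downside is a smaller and more selected denominator for the symptom-free share. It shrinks further as vaccination and antibody positivity rise (Section 9.6.1 already puts more than 97% above the standard threshold) and as the anti-N assay is limited to a subset from protocol v16.0.

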© Copyright: The University of Oxford and Oxford University Hospitals NHS Foundation Trust 2019 Page 24 of 113 At every assessment (contact or non-contact home visit or self-completion), all participants will take a self-swab of their nose and throat and complete a short questionnaire (online or by telephone from protocol v16.0). The self-swab can be done by those aged 12 years and older and has been successfully used in drive through testing centres; those 2-11 years will be swabbed by their parent/carer. The swab is the same size as that used routinely in paediatric practice and there is no modification to the technique needed. Self-swabbing minimises the risk to study workers of contracting SARS-CoV-2 from an asymptomatically infected individual at a home visit. In a subset of households, optional consent will also be sought for adults aged 16 years or older to have a blood draw. In the first cross-sectional survey (Phase I, see below), the invitation to undergo additional blood sampling was sent to those sampled from the ONS Opinions COVID-19 Survey for practical reasons and to enable future data linkage to more detailed data on reported self-isolation behaviours. In subsequent surveys, of the 6,000 households invited to participate each week (24,000 per month), approximately 600-1200 households per week (2,400-4,800 per month; 10%-20%; including 200-400 households per month from each of Wales and Northern Ireland) will be randomly selected to receive an invitation for adults aged 16 years and older in the household to have a blood draw, as well as for all individuals 2 years and older to self-swab, targeting enrolment of a minimum of 300 households per month for blood sampling (10% of the target enrolment; including at minimum 50 households per month from each of Wales and Northern Ireland). From the end of July 2020, the percentage randomly selected to receive an invitation for blood draw was increased to 20%, to assess the potential for prior immunity to affect future infection. In order to monitor the impact of vaccination on both immunity and infection, from February 2021, we asked a representative sample of those already recruited to the study but only giving swabs to also give blood at their monthly visits, and for everyone giving blood samples to stay in the study until April 2022 (i.e. to have additional visits beyond their original 12 month study period). The blood target from April 2021 to March 2022 was to achieve up to ~125,500 adults 16 years and older with blood test results every month in England, and up to ~7,500, ~4,500 and ~12,500 per month in Wales, Northern Ireland and Scotland (~150,000 in total across the UK). All households who are approached for blood sampling will be included in the blood sampling cohort if anyone in the household is willing to provide consent for blood draws, and blood will be drawn from all participants in the households selected for blood sampling who are willing to provide blood, so the precise percentage randomly selected to receive this invitation to provide blood samples will be adjusted based on opt-in rates. If participants consent to serial sampling, blood will also be drawn monthly for the duration of their consented serial sampling. The choices available to participants are illustrated in Figure 2. Where an adult in the household is already giving blood, from September 2021 we will also ask children and young people aged 8-15 years whether they would be happy to give a sample of blood (5-7 years in an initial pilot in October 2021 only). For those aged 8-15 years, from December 2021 to March 2022 the target is to achieve ~3,600 blood test results from older children/adolescents every month.

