16.8. Expenses and Benefits

Up to 1 April 2022, a small compensation (£50 voucher) will be offered to each consenting/assenting participant (including child participants) for each completed enrolment home visit (contact or noncontact) to reflect their time and inconvenience. For each subsequent completed serial sampling home visit, each participant will be offered a £25 voucher. This includes any additional visits after 12 months for those invited to extend follow-up for additional monthly visits through to April 2022. Vouchers can be posted to participants, but we will offer them the option of receiving the vouchers more quickly by email if they are happy to provide an email address for this purpose (email can also be used to receive test results and study updates). The total compensation per participant would therefore be £50 for a single visit, £150 for five visits over one month and £425 for 16 visits over one year; those consenting to additional monthly visits up to April 2022 would receive £425 plus or £25 for each extra visit up to April 2022 (total depending on date of original household enrolment).

Children and young people aged 5-15 years who attempt a blood draw for finger prick testing will receive a sticker as a "thank you" in the initial phase. Feedback from children and their parents in the initial phase indicated that this was not helpful or necessarily wanted and therefore stickers will not be given in the main phase of antibody testing in children and young people aged 8-15 years (those aged 5-7 years no longer included from protocol v13.0).

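### The quantitative antibody regression names only an optional household effect and no vaccination term; fitted as written to monthly readings it understates uncertainty and leaves the anti-S curve open to confounding

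*Protocol*

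**What the plan says.** Section 11.2 states: "Random effects linear regression models will also be generated for the absolute optical density readings", possibly log-transformed, "in relation to time since onset of first symptoms, with those not reporting symptoms treated as an additional category". The random structure is given in one parenthesis: "random effect per household – may be omitted depending on model fit". The covariates follow: "Additional factors considered in these models will include age, sex and ethnicity".

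Elsewhere the protocol says:

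- **Repeat sampling (Section 7).** For participants on serial sampling, "blood will also be drawn monthly for the duration of their consented serial sampling". Over 95% of participants chose long-term monthly visits.
- **Clustering (Section 11.4).** Analyses are to adjust for household clustering wherever possible. Participant-level clustering is not mentioned.
- **Household association (Section 6).** A secondary objective is the association of immunity between household members. A footnote says this will be estimated from random effects models and points to Section 11.
- **Vaccination.** Section 5 says that vaccines produce antibody to spike only. Section 9.6.1 asks at each assessment "Have they received or been offered a vaccine against COVID-19", with type, number of doses and dates.
- **No separate plan (Section 11.1).** The statistical aspects are summarised in the protocol, and there is no formal SAP.

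**The concern.** Two separate features of this model matter.

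The first is dependence. Monthly readings from one person are correlated beyond what the household shares. A household intercept gives two readings from the same person the same correlation as two readings from different members of the household. The model therefore counts repeat samples as more independent information than they are. Section 11.7 says that results will be interpreted from their 95% confidence intervals, so interval coverage matters directly.

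The second is confounding. Someone with symptoms in 2020 and vaccine doses in 2021 gains anti-S as time since symptoms increases. Without a vaccination term, that rise is attributed to time since symptoms, in an analysis meant to describe the antibody course after infection. Section 11.3 gives monitoring of antibody decline as the reason for cutting the blood targets less than the swab targets.

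The option to drop the household effect raises a further point: it would remove the quantity that a secondary objective asks for.

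**Working it through.** The protocol gives no standard error, power or sample size for this model, so there is no stated figure to reproduce. It also gives no variance components or vaccine effect. Those used below are assumptions.

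**1. Samples per person.** Section 16.8 gives £"425 for 16 visits over one year", and 50 + 15 × 25 = 425 agrees. The 16 visits are enrolment, weeks 1 to 4 and months 2 to 12. Weeks 1, 2 and 3 have no blood draw, so there are 16 − 3 = 13 blood timepoints in a full year.

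**2. Person-level factors (such as sex), all correlation ignored.** Design effect = 1 + (m − 1) × ICC, and the standard error is too small by its square root.

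| ICC | m = 13: design effect | factor | m = 4: design effect | factor |
|---|---|---|---|---|
| 0.3 | 4.6 | 2.1 | 1.9 | 1.4 |
| 0.5 | 7.0 | 2.6 | 2.5 | 1.6 |
| 0.7 | 9.4 | 3.1 | 3.1 | 1.8 |
| 0.9 | 11.8 | 3.4 | 3.7 | 1.9 |

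**3. Does the household effect repair it?** Simulation: 400 replicates of 400 households × 2 people × 13 monthly samples. Log-OD standard deviations were participant 0.7, household 0.4 and residual 0.5. Time since onset at first sample was uniform over 0 to 6 months, the true slope was −0.05 per month, and there was no vaccination.

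| Model | Term | Model SE / empirical SD | 95% coverage |
|---|---|---|---|
| No random effect | sex | 0.32 | 46% |
| Household only | sex | 0.29 | 40% |
| No random effect | time slope | 0.71 | 84% |
| Household only | time slope | 0.74 | 87% |

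The household effect makes little difference. A smaller simulation with other variances (0.2 household, 0.4 person, 0.4 residual; 150 households × 2 people × 12 samples; 80 replicates) gave 0.0432 / 0.0178 = 2.4 with the household effect and 0.0426 / 0.0167 = 2.6 without it. Coverage was 63% and 65%, with Monte Carlo error of about 5 points.

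**4. Why the slope is hit less.** Time since symptoms varies within a person (months 0 to 12, variance 14) and between people (uniform over 6 months, variance 3), 17 in total. The between-person variance component is 0.49 + 0.16 = 0.65 and the residual is 0.25. With no random effect, model SE / true SE = √[(0.90 × 17) / (13 × 3 × 0.65 + 17 × 0.25)] = √(15.3 / 29.6) = 0.72, which matches the simulation. The ratio falls below 1 only when the between-person share of the variance in time exceeds 1/13; here it is 3/17. The factor of about 1.4 (1/0.72) therefore belongs to this scenario.

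**5. Vaccination omitted, anti-S.** Let vaccination occur at a uniformly random month in the 12 and add δ to log OD. The bias in the slope is δ × Cov(vaccinated, time) / Var(time) = δ × (14/12) / 17 = 0.0686δ. The fitted slope is then −0.05 + 0.0686δ:

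- δ = 0.5 gives −0.016.
- δ = 0.73 gives about 0.
- δ = 1.5 gives +0.053.

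Simulation at δ = 1.5 gave +0.053 with no random effect and +0.062 with the household effect. Adding a vaccination term gave −0.050.

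**6. The household variance itself.** With variances 0.2, 0.4 and 0.4, two people and 12 samples, the expected mean square between households is 24 × 0.2 + 12 × 0.4 + 0.4 = 10. Within households it is (5.2 + 22 × 0.4) / 23 = 0.609. A household-only model then estimates (10 − 0.609) / 24 = 0.39 against a true 0.20. Dropping the effect loses the household association; keeping it without a participant effect inflates it.

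**The case against.** The best defence is that Section 11.2 is a summary that does not fix the analysis dataset or the full random structure. It calls these random effects models and then makes the household effect optional. If household were the only random effect, dropping it would leave no random effects model, so a participant effect may be intended. Section 11.2 also points to an external methods article that is not available here. This stands as far as intent goes. A reader might infer that the standard errors and the curve are simply wrong, and the text does not support that; the fault is conditional on fitting the model as written. But no participant effect is stated anywhere, and Section 11.4 also speaks only of household.

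On vaccination, the factor list is open-ended, and an exploratory objective in Section 6 names vaccination among the characteristics for the immunity analyses. So a reader who infers that vaccination is excluded goes too far. Against this, the infection models in the same section expressly take in the other questionnaire responses, where vaccination is recorded, and the antibody model does not. The argument also cannot extend to anti-N, which on the protocol's account vaccines do not raise.

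It is also fair to say that a household effect of material size would usually survive a fit criterion, and that dropping it barely changes the standard errors in question. That limb therefore rests on the conflict with Sections 6 and 11.4, not on the size of the standard errors.

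Finally, immunity is estimated mainly by threshold-based spatiotemporal MRP, and the blood targets rest on margins of error for seropositivity. This limits the importance of the point.

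**Conclusion.** The point holds in conditional form. If the model is fitted as written to all serial readings, standard errors for person-level factors are too small whenever within-person correlation is positive. The factor is about 2.1 to 3.4 with 13 samples and about 1.4 to 1.9 with 4, for assumed correlations of 0.3 to 0.9. For the slope on time since symptoms it was about 1.4 in one simulated scenario, with coverage of 84% to 87%. It would be wrong to carry the larger factors over to the slope, whose factor depends on how widely onset dates are spread between people.

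The anti-S curve is open to confounding by vaccination. A reversed sign is possible but not established, because it depends on a vaccine effect and timing that the protocol does not give.

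The option to omit the household effect ("may be omitted depending on model fit") conflicts with Section 11.4 and with the Section 6 objective on household immunity, since this is the only model in Section 11.2 that names a household effect.

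This is a supporting analysis. The primary MRP analysis of swab positivity and the sample size are untouched.

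**What to change.** In Section 11.2:

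- Specify random intercepts for participant nested in household.
- Retain the household effect by design and delete the option to omit it on fit. This restores agreement with Sections 6 and 11.4.
- For anti-S, include time-updated vaccination status: number of doses, type and time since last dose.
- Optionally, as a sensitivity analysis, restrict to samples taken before vaccination, or use anti-N. The first selects people by age and calendar time, because vaccination depends on both. The second is limited from April 2022, when anti-N is assayed only in a subset.

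A participant random slope, or censoring at first dose as the main estimate, is a debatable choice and is not needed to meet this point.

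The cost is one paragraph. The vaccination data are already collected under Section 9.6.1. The downside is slightly more model complexity and run time.
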